## **1.6 Hypothesis**

The following hypotheses guided the study:

- $H_1$ : A KC-EP can improve perception, knowledge, and perceived barriers in relation to KC, and levels of stress among mothers.
- $H_2$ : KC is effective in improving weight gain patterns, LOS, and breastfeeding rates among premature infants.
- $H_3$ : A KC-EP can improve nurses' perception, knowledge, and practice in relation to KC implementation.

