### **3.16 Data Collection Method**

There were three phases to this study: Phase I, Phase II, and Phase III. Phases included:

i)In phase, I, the data ( $T_0$ ,  $T_1$ , and  $T_2$ ) for the control group of mother-infant dyads was collected within six months until the data met the requirements of the study. Data collection for the control group's mother-infant dyads started in early February 2018, and continued until the end of July 2018. Assessment of function in routine clinical practices in the control group of mother-infant dyads and outcomes of premature infants was recorded in the KCPR booklet provided for the control group of mothers within the stipulated time and then analysed.

ii)In phase II, one group pretest-posttest for nurses' data collection process was conducted 2 months after the control group of mothers' data collection was completed. The data collection for nurses and the intervention commenced in early August 2018 and continued to the end of September 2018. Quantitative data (Questionnaire II) were collected at pretest, and one week after the structured KC-EP was conducted for nurses the posttest data were analyzed. The structured KC-EP for nurses included knowledge, skills, and attitude prior to KC guidelines and protocol. The specific aims were to educate nurses in the content areas noted above. The reasons for implementing a neonatal KC protocol for mother-infant dyads were generally considered in terms of the method of holding the premature infant directly, breastfeeding rates and looking at the effects of KC outcomes.

iii) In phase III, the data ( $T_0$ ,  $T_1$ , and  $T_2$ ) for the experimental group of mother and premature infant were collected within seven months. In the experimental group, data collection for mother-infant dyads began in early October 2018 and was completed by the end of April 2019. The KC-EP for mothers was conducted by the nurses in the NICU for them to implement KC with their premature infants. The structured KC-EP was comprised of theory and practical sessions to fulfill the objectives of this study. The post-intervention assessment

of quantitative data (Questionnaire I) on mother-infant dyad compliance and outcomes of KC implementation (KCPR) commenced from the premature infant's recruitment day. The data was plotted to begin from the inclusion criteria age until 3-months-old corrected age.

[figure not shown]

Figure 3.2: Flow Chart Showing the Three Phases of Data Collection

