### **3.17 Method of Data Collection for Nurses**

The nurses were screened and recruited based on universal sampling. Method of data collection for nurses was similar to that for mothers, whereby, prior to the KC-EP for nurses, pretest data on nurses' perception, knowledge, and practice were collected using the KCQ tool in Questionnaire II. The data for nurses were collected within a 2 month period from 1st August 2018 to 30th September 2018 for the pretest-posttest groups of nurses. The researchers briefed the nurses and encouraged them to take part in the study by presenting verbally brief information to the head nurse in charge of the unit, with two forms of consent given to the nurses on the same day as the pretest program. All nurses who attended were recorded with their name, identification code number, date of attendance and signature in order to plan the date for their following posttest. To ensure confidentiality and privacy, each returning questionnaire was assigned an identification code number. The consent form together with the questionnaire was stamped, starting with nurse 01(N01), with the code number in the top right corner. If the nurses refused to continue with the study, they were instructed to notify the researcher and ask for a withdrawal. Upon receiving an application for withdrawal from the study, the researcher found and destroyed the questionnaire, which was submitted based on the code number. The pretest (Questionnaire II) was given to all nurses before the KC-EP was administered to them. The nurses were instructed to complete Questionnaire II, which took approximately 15 to 20 minutes to complete, without reference to any resources before the KC-EP session for nurses was conducted. Nurses were asked to return the questionnaires upon completion, with one copy of the informed consent. All nurses were advised to keep one copy of the informed consent for their records. Following the completion of the KC-EP, the nurses were told of the posttest sit after the 7th day of the pre-test and intervention program. The same structured Questionnaire II was administered to the nurses at the posttest. Data collection among nurses was conducted within the stipulated time.

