### **3.19.1 Analysis of Quantitative Data**

Graduate Package 23.0 of the Statistical Package for Social Sciences (SPSS) provided tools to analyze the data required to achieve the research objectives:

In the pretest of dependent variables, data from the mothers and infants were evaluated for homogeneity, normality, variability, and data normality in the pretest. Nevertheless, the variance test for the nurses' data was not homogeneous since we were dealing with the same group, the data were normally distributed and the variances between the groups were equal, and the sample size was acceptable (no less than 30 cases per group). The number and proportion were stated as continuous variables and categorical variables. Continuous variables were compared for normally distributed variables ('mothers' and 'infants') using the independent t-test and variance analysis (ANOVA/ANCOVA). Pearson's chi-square test was used because the independent variables were nominal categorical variables. The Chi-square test was applied with normally distributed data to establish associations between independent variables, such as age, years of service as RN, years of working in NICU and educational qualification level, and dependent variables: perception, knowledge and outcomes improvement: weight gain, length of hospitalization stay and breastfeeding rates. In addition, the Shapiro-Wilk test was used to test data normality for both the pre and post-test, as the sample was below 50 per arm. To assess the effect of the structured kangaroo care educational program (KC-EP) on mothers', infants' and nurses' outcomes, for the data on mothers, infants and nurses, the general linear model (GLM) univariate analysis of variance and covariance analysis was used. GLM and repeated measures were used to analyze the main effects and interaction effects of KC outcome variables, and to examine the hypotheses of the outcomes.

Table 3.4: Summary of Statistical Analysis of Quantitative Data Plan

No.	Objectives	Measurement Variables	Statistical analysis

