1.	Are there any statistically significant differences in mothers' perception, knowledge, perceived barriers regarding KC, and stress related to 'premature infants admission to NICU' after participation in the KC-EP?	Perception, knowledge, perceived barriers and stress related to premature infants' admission to NICU mean scores Effect of KC-EP KC performance (Ordinal data)	Descriptive - mean, SD, skewness and kurtosis Chi-square test, GLM, repeated measure (RM) & Pearson Eta Squared.
2.	Does kangaroo care improve weight gain patterns in premature infants between control and experimental groups at $T_0$ , $T_1$ , and $T_2$ ?	Weight gain patterns (grams) mean score KC compliance Duration (hours/weeks) Frequency and Percentage (Continuous data)	Descriptive – mean, SD, skewness and kurtosis Chi-square test, GLM and t-test.
3.	Does kangaroo care decrease the length of hospitalization stay for premature infants between control and experimental groups?	Length of hospitalization stay Frequency and percentage (Continuous data)	Descriptive – mean, SD, skewness and kurtosis Chi-square test, GLM and test
4.	Does kangaroo care improve breastfeeding rates for premature infants between control and experimental groups?	Breastfeeding rates KC compliance Frequency and percentage (Continuous data)	Descriptive – mean, SD, skewness and kurtosis Chi-square test, GLM and t-test.
5.	Are there any statistically significant differences in nurses' perception, knowledge, and practice regarding KC before and after participation in the KC-EP?	Perception, knowledge, practice mean scores Effect of KC-EP (Ordinal data)	Descriptive - mean, SD, skewness and kurtosis Independent t-test GLM, RM & Pearson Eta Squared.

The key influence of an explanatory variable is its direct effect on the outcome variables (Field, 2011). Additionally, the effects of covariate and covariate interaction with KC can be included in GLM univariate analysis. This covariance analysis is an extension of the variance analysis to include a covariate/confounder component (Field, 2011). This covariance is linearly related to the dependent variable, and its inclusion in the analysis will minimize the error associated with the covariance analysis (Field, 2011). The test is appropriate since

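### Table 3.4 row 5 lists an independent t-test for the before-after comparison of a single group of nurses, and the plan does not say which of the listed analyses is reported

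*Combined protocol and SAP*

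**What the plan says.** Row 5 of Table 3.4 poses the nurses' question as a before-after comparison of perception, knowledge and practice, and gives as methods "Independent t-test GLM, RM & Pearson Eta Squared". This is the analysis row for H3 in section 1.6: "A KC-EP can improve nurses' perception, knowledge, and practice in relation to KC implementation".

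The design is stated in section 3.16, phase II: "one group pretest-posttest for nurses' data collection process". Section 3.19.1 confirms it when it explains how the nurses' data differ from the other data, "since we were dealing with the same group". Section 3.17 has the same Questionnaire II answered at both times.

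The text of section 3.19.1 says three further things that bear on row 5:

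- The independent t-test is assigned to two populations, neither of them nurses: "Continuous variables were compared for normally distributed variables ('mothers' and 'infants') using the independent t-test".
- A univariate general linear model is named for all three populations: "for the data on mothers, infants and nurses, the general linear model (GLM) univariate analysis of variance".
- The hypotheses are to be examined with GLM and repeated measures: "repeated measures were used to analyze the main effects and interaction effects of KC outcome variables, and to examine the hypotheses of the outcomes".

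**The concern.** An independent t-test compares two samples of different people. For the nurses' change over time there is one sample, seen twice. The test treats each nurse's two scores as unrelated, so it ignores the part of the variation that cancels when a nurse is compared with herself.

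Row 5 is the only row of Table 3.4 that writes the word independent, and it is the only row about one group. The two-group infant rows on weight gain and breastfeeding (rows 2 and 4) say only t-test.

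The stake is the standard error and confidence interval for the nurses' mean change. With a positive pre-post correlation both would be too wide, and a modest change could be missed. This happens only if the independent t-test is the reported result, or a univariate GLM with time as a between-subject factor. If the repeated-measures result is reported, nothing is lost. The plan does not say which it will be.

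**Working it through.** **No plan figure to reproduce.** Section 3.7.3 invites all 46 nurses and 1 head nurse, so at most 47 pairs, with no power calculation. The end of section 3.19.1 sets two-sided tests at 0.05. No pre-post correlation or expected effect is given for the nurses, so r is shown over a range.

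**Formula.** With equal SDs s and n pairs, the true variance of the mean change is 2s²(1 − r)/n. The independent test uses 2s²/n. Hence:

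- SE ratio, independent to paired = 1/sqrt(1 − r)
- True size of the nominal 5% test = 2[1 − Φ(1.96/sqrt(1 − r))]

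| r | SE ratio | True size (formula) | Simulated, 47 pairs |
|---|---|---|---|
| −0.2 | 0.91 | 7.4% | 7.3% |
| 0 | 1.00 | 5.0% | 5.0% |
| 0.2 | 1.12 | 2.8% | 2.7% |
| 0.41 | 1.30 | 1.1% | 1.1% |
| 0.51 | 1.43 | 0.5% | 0.5% |
| 0.7 | 1.83 | 0.03% | 0.05% |

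The paired test stays close to 5% at every r tried.

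**Where 0.41 and 0.51 come from.** Section 2.4.1 describes a pretest-posttest study of a nurse training course, with t on 54 and 53 degrees of freedom. If those tests are paired, there were 55 and 54 pairs.

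- Knowledge: change 88.54 − 78.7 = 9.84. SD of change = 9.84/9.1 × sqrt(55) = 8.02. r = (8.30² + 6.13² − 8.02²)/(2 × 8.30 × 6.13) = 0.41. Effect = 9.84/sqrt((8.30² + 6.13²)/2) = 1.35 SD.
- Skills confidence: absolute difference 32.06 − 26.80 = 5.26. SD of change = 5.26/8.459 × sqrt(54) = 4.57. r = (3.49² + 5.22² − 4.57²)/(2 × 3.49 × 5.22) = 0.51. Effect = 1.18 SD.

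The skills figures carry a sign conflict. The knowledge mean rises and the skills mean falls from pretest to posttest, yet both t values are negative. Only the absolute difference is used here, and the sign does not affect r. The study used another instrument and reports 68 nurses, more than the degrees of freedom imply, so these values are a guide only.

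**Interval width with 47 pairs and that study's SDs (95% half-widths).**

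- Knowledge: independent, t(92) × sqrt((8.30² + 6.13²)/47) = 2.99 points; paired, t(46) × 8.02/sqrt(47) = 2.35 points.
- Skills confidence: 1.82 against 1.34 points by the same formulas.

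With these unequal SDs the SE ratios are 1.29 and 1.37.

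**Power.** At 1.35 and 1.18 SD both tests have simulated power of about 100% with 47 pairs, so the decision is the same. A loss needs a smaller effect. As an illustration only, under an assumed change of 0.4 SD, simulated power is 48% (independent) against 70% (paired) at r = 0.41, 48% against 77% at r = 0.51, and no loss at r = 0.

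**The case against.** The strongest reply is that a valid analysis is already planned. The same cell lists GLM and repeated measures, and the text says these examine the hypotheses, which include H3. On that view the independent t-test is a surplus label in a summary table. The reference list even contains an item on checking normality for a paired t-test, which suggests a labelling slip. This stands as a limit on the harm. It does not remove the entry, and it does not tell the analyst which of the listed results to report.

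A second reply is that the independent t-test may be meant for nurse subgroups. Section 3.10.1 plans to look at nurse characteristics, and Appendix H has two-level items such as the neonatology certificate. But row 5 asks a before-after question, section 3.19.1 gives associations of this kind to the chi-square test, and no section states the subgroup use.

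A reader might go further and infer that time will be entered as a between-subject factor, because a univariate GLM is named for nurses. No section says so; the form of the GLM is simply left open. A reader might also infer that pretest and posttest forms cannot be linked. The documents point the other way: section 3.18 has code numbers on both sets, and in section 3.17 attending nurses were "recorded with their name, identification code number, date of attendance and signature in order to plan the date for their following posttest". Linking is a strong inference for nurses, though only for mothers (section 3.16.1) is it stated outright.

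**Conclusion.** The entry is wrong as written, and the point is minor. The before-after comparison has one nurse group, and the plan's own text gives the independent t-test to other populations. A valid method stands in the same cell, but the plan does not name it as the reported one.

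The consequence is conditional on the wrong result being reported. For r between 0.41 and 0.51 with equal SDs, the standard error would be about 1.3 to 1.4 times too large and the true size about 1.1% to 0.5%. This rests on reading the outside study's t-tests as paired and on carrying its correlations over to this study.

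Two stronger conclusions are tempting and not supported. One is that the error is always conservative. That holds for positive r; the test has the right size only at r = 0 and is slightly liberal if r is negative (about 7.4% at −0.2), although a negative correlation is unlikely for the same questionnaire repeated after about a week. The other is that the nurses' analysis would lose its power. At the only nurse-training effects from which a size could be derived here, the decision is unchanged and only the interval is too wide. A power loss needs a smaller effect, which the documents do not give.

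**What to change.** Three small edits:

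1. In Table 3.4 row 5, replace the independent t-test entry with: *paired t-test (equivalently, the two-level repeated-measures GLM without covariates) on pretest and posttest scores matched by nurse code; this is the main test for H3. Report mean change with 95% CI, the number of complete pairs and the number unmatched.*
2. In the text of section 3.19.1, add: *For nurses, time (pretest, posttest) is a within-nurse factor; the univariate GLM wording does not apply to the nurses' before-after comparison.*
3. In section 3.17, add one line stating that the nurse code is used to match pretest and posttest, as section 3.16.1 already does for mothers.

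The cost is one table cell and two sentences. No new data are needed, provided the codes on the two nurse forms can be linked as sections 3.17 and 3.18 suggest.

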### **3.19.2 Pre-testing**

Pre-testing of the instrument is an important stage since pre-testing results will indicate whether the survey can meet the study's objectives (DeMaio, Bates, Ingold, & Willimark, 2006). Pre-testing was performed in this study to verify the accuracy of the directions and items in the questionnaire. The objectives of the questionnaire pre-test were:

- To detect the uncertainties, misinterpretation, or other inadequacies in the questionnaire.
- To estimate the time required to answer the various items in the questionnaire.
- To ensure the time required to answer the various items in the questionnaire.
- To ensure that it does not contain any sensitive questions.
- To improve the reliability, quality and validity of the instrument and
- To identify any weakness in structure and instrumentation (Cooper, Schindler, & Sun, 2003)

There was one panel of experts, which included two neonatologist consultants and two senior nurses lecturers with a Ph.D. In Nursing, 3 neonatal nurses were required to check the content and face validity of the KCQ and PSS questionnaires: NICU: P&R questionnaire; the leaflet and booklet were checked and vetted for spelling errors, grammatical structure, unclear instructions or items, time taken for completion and the reliability estimation.

### **3.19.3 Validity**

Validity refers to how well the measuring instrument measures the test principles of a research study (Burn & Grove, 2009). The first set of questionnaires was adapted from a validated questionnaire developed by Ludington-Hoe et al., (1999); Angler & Brumbaugh et al., (2013). An expert panel examined, reviewed and judged the contents and face-validity of the instruments. The panel, consisting of seven health professionals with expertise in neonatology care and including two neonatologists, two senior nursing lecturers and three senior staff nurses certified in neonatology, reviewed and commented on the consistency, accuracy, and relevance of the instrument to clinical practice, validity, and comprehensiveness of content. As recommended by the experts, revisions were made: items were reworded, and improvements were made to the sentence structure. Nevertheless, this study used only 80 items from the quantitative questionnaire.

The second set of instruments was adapted from a validation tool developed by Miles et al., (1992). Revisions were made as proposed by the panel of experts which consist of a neonatologist, and two nursing lecturers ( one with neonatal nursing certificate) . Items were rephrased and the sentence structure was improved, although a few variables were introduced on demographic characteristics. After Questionnaire II (for nurses) and Questionnaire I (for mothers) had been validated, it was translated into Malay, as the national language, so that participants can understand the questionnaire. Content, face validity, forward and backward translation were done to ensure the semantic equivalence of the instruments; flip charts (English and Malay versions), the leaflet and the KCPR booklet were also validated by an expert panel consisting of seven persons, five from the neonatal unit, in a teaching hospital and two from the Nursing Department, University Malaya. The panel reviewed and commented on the instruments' relevance to clinical setting practices.

### **3.19.4 Reliability**

The reliability of the instrument was measured by its stability and equivalence. The reliability of the content and construction of the questionnaire in this study were tested during the pilot study. A pilot study was conducted on 30 mothers and 50 nurses to test the reliability for the total population. The sample of mothers was collected from respondents in the NICU at UMMC. The same set of questionnaires was used twice to assess perception, knowledge, perceived barriers and stress. Cronbach's alpha ( $\alpha$ ) was 0.813 for the perception subscale; 0.873 for the perceived barriers subscale; 0.951 for the sub-scale of stress. Furthermore, KR20 for the knowledge subscale was 0.785. The researchers assumed that the translated KCQs and PSS: NICU: P&R instruments were reliable during the internal consistency test. The Content Validity Index of the KCQs Malay version was 0.95, which was considered acceptable. Reliability ensures an instrument has consistent and dependable scores (Creswell, 2005). In reliability values, the indicators to be measured are Cronbach alpha ( $\alpha$ ) value, person reliability value, individual measurement, and relevant responses (Azrilah Abdul Aziz, 2010). Fraenkel and Wallen (1996) reported that the reliability of an item would be accepted if the alpha is between 0.70 and 0.99, while Kubiszyn and Borich (2000) indicated that an  $\alpha$  value within the range between 0.80 and 0.90 should be acceptable.

The data was analyzed using descriptive statistics, The frequency for continuous data, general linear model, and repeated measure was used for categorical data and mean (standard deviation). The statistical analysis was carried out using version 23.0 of the SPSS. The participants were assured of confidentiality and that the safety of the mothers and premature infants was maintained. Care was taken that there was no exploitation of human rights, humanity or discrimination of any type. Ethical clearance from the teaching hospital's ethical committee was also granted before the study began.

### **3.20 Pilot Testing**

There were two pilot tests conducted: one to test the questionnaire's validity and reliability, and the other to determine the study's feasibility in the actual clinical setting. A pilot study was also carried out to test the reliability of the KCQs tool Malay version. For the perception section the Cronbach's  $\alpha$  was 0.813 to 0.880, the knowledge section 0.793 to 0.785, the practice section 0.841, the barriers section 0.873, and the stress section 0.951. The researchers concluded that the translated KCQs were reliable during the internal consistency test. The Content Validity Index of the KCQ's Malay version was 0.970, which was deemed acceptable.

